2.4 Population and Sample

2.4.1 Inclusion and Exclusion Criteria

1) Inclusion Criteria

- a. Pregnant women aged 19-35 years old;
- b. Gestational age 7-13 weeks at the time of the screening process and be willing to take part in an intervention study at 8-14 weeks gestation;
- c. Permanent residents who will stay in the research area for the following 1 year.

2) Exclusion Criteria

- a. Mothers who have chronic diseases such as hypertension (blood pressure \geq 140/90 mmHg) or under treatment for hypertension, diabetes (non-fasting blood sugar when >200 mg/dL) or under treatment for diabetes, hypercholesterolemia (blood total cholesterol >240 mg/dL), hyperuricemia (blood uric acid > 6 mg/dL), have had a history of tuberculosis or under treatment for tuberculosis or under treatment for other chronic diseases that requires a long treatment, such as cancer, heart disease, epilepsy, etc.;
- b. Have a history of preeclampsia/eclampsia and gestational diabetes in their previous pregnancy;
- c. Have a risk of chronic energy deficiency (mid-upper arm circumference < 23.5 cm);
- d. Have severe anemia (hemoglobin < 70 g/L);
- e. Have a history of allergy to chicken liver and/or eggs.

3) Drop-out criteria

- a. Preeclampsia, eclampsia;
- b. Dead infant/stillbirth;
- c. Twin delivery;
- d. Infants are born with congenital anomalies;
- e. Infants are not breastfed.

4) Other criteria

If an infant is born with Low Birth Weight (LBW) or is premature, then the infant will not be included in the measurement of breast milk volume and

assessment of exclusive breastfeeding status with Deuterium Oxide Dose-to-Mother Technique. However, the growth and data collection such as anthropometry and ages and stages questionnaires (ASQ-3) will still be carried out.

[figure not shown]

Figure 1 Study designs. MEC: Micronutrient-enriched Crackers.

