2.4.2 Population and Sample size calculation

The population of this study are the people who live in the area of Pamulihan, Sukasari and Tanjungsari Sub-Districts, Sumedang District, West Java. All parameters used in calculating sample sizes can be seen in Table 1. Design effects, cluster/village, are estimated using previous data collected in the same area.

- 1) Phase 1: To detect a 1 cm difference in birth length between the intervention and control groups (this is approximately 0.5 SD from the WHO Growth Chart (2007)), with power of 0.90, statistical significance of 0.05, and design effect of 1.1 due to village clusters, a minimum sample size of 228 is required (114 in each group) (to be presented in tabular form).
- 2) Phase 2: Based on an average growth velocity of 3-3.2 cm/month, and to detect differences in growth velocity of 0.70 cm between the intervention and control groups, with power of 0.80, statistical significance of 0.05, assuming a standard deviation of 2.2 cm/month, a within-person correlation of 0.73 and a design effect of 1.1 due to village clusters, a sample size of 162 would be required (81 in each group) (to be presented in tabular form).

As the primary outcomes for Phase 1 require a sample size of 228, then 11 participants from 22 clusters will be required. However, we aim to recruit 11 participants from 28 clusters, giving a sample size of 308. This will allow for exclusion due to stillborn or premature birth (~10%, i.e., n~15 in each group) and drop-out or loss-to-follow-up of approximately 15%, so the total sample size is 324. For Phase 2, if 231 participants are retained, a further 1-5% may fail to breastfeed their infants, giving a final sample size of 219-228 to assess Phase 2 outcomes. This sample size will also permit the detection of the differences in the secondary outcomes also specified below (Table 2), in addition to the primary outcomes.

Table 2. Parameters used in calculating sample sizes for secondary outcomes

Measure	Observed mean	Observed SD	Difference to detect	ICC	Design effect	Sample size**
Birth length (cm) ^a	49.7	2.2	1.0	0.010	1.10	114
Infant length at 5 months (cm) ^a	63.0	2.2	1.0	0.010	1.10	114
Birth weight (g) ^a	3013	514	200	0.010	1.10	116
Haemoglobin at 3 rd trimester (g/dL) ^b	12.6	1.2	0.5	0.048	1.48	132
Volume of breast milk at 5 months post-partum (mL/day) ^c	787	148	70	0.010	1.10	80
Micronutrient concentrations of breast milk at 5 months post-partum (Vit A, µg/L) ^c	634	281	130	0.036	1.36	102

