Maternal diet at 5 months post-partum (Vit A, µg RAE/d) ^d	478	244	110	0.010	1.10	87
Maternal micronutrient status at 5 months post-partum (Ferritin, µg/L) ^e	35.8	29.7	13.0	0.010	1.10	91
Infant micronutrient status at aged 5 months (Ferritin, µg/L) ^e	46.7	35.6	15.0	0.010	1.10	99

*ICC: intra-class correlation

*Design effect: based on the average size of cluster= 11

**Required sample size per group with 80% power and alpha= 0.05

^aData from observation by Diana A, Mallard SR, Haszard JJ, Purnamasari DM, Nurulazmi I, Herliani PD, et al. Consumption of fortified infant foods reduces dietary diversity but has a positive effect on subsequent growth in infants from Sumedang district, Indonesia. PLoS One. 2017 Apr; 12(4):1-17;

^bData from observation by Diana A, Haszard JJ, Purnamasari DM, Nurulazmi I, Luftimas DE, Rahmannia S, et al. Iron, zinc, vitamin A, and selenium status in a cohort of Indonesian infants after adjusting for inflammation using several different approaches. Br J Nutr. 2017 Nov; 118(10):830-839;

^cData from observation by Daniels L, Gibson RS, Diana A, Haszard JJ, Rahmannia S, Luftimas DE, et al. Micronutrient intakes of lactating mothers and their association with breastmilk concentrations and micronutrient adequacy of exclusively breastfed Indonesian infants. Am J Clin Nutr. 2019 Aug; 110(2):391-400;

^dData from observation by Rahmannia S, Diana A, Luftimas DE, Gurnida DA, Herawati DMD, Houghton LA, et al. Poor dietary diversity and low adequacy of micronutrient intakes among rural Indonesian lactating women from Sumedang district, West Java. PLoS One. 2019 Jul; 14(7):1-13;

^eUnpublished data

3. Study Goals and Objectives

This will be the first RCT in Indonesia to examine the effect of daily maternal consumption of MEC on birth length and infant linear growth; earlier interventions have examined only birth weight.

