4.2 Statistical Analysis

Primary analyses will be by intention to treat. The mean number of crackers consumed overall and compliance rates will be examined. Only live born infants will be included in all analyses. Intervention groups will be compared using mixed effect regression models using cluster (village) as a random effect. Main outcomes for analyses for phase 1 are birth length and for phase 2 are attained and incremental linear growth at 5 months post-partum. Analyses for phase 2 will be conducted with adjustment for weight-for-age and breastfeeding practice (exclusively/partially breastfeeding), where appropriate. Model assumptions will be checked using standard procedures and variables log transformed when necessary. Guidelines for reporting will be followed, as outlined in the Consolidated Standards of Reporting Trials (CONSORT) statement: extension to cluster randomised trials.

Given the short period of data collection and the anticipation that no highly potential harm/risks will be expected, the study will continue until the end of data collection without data interim analysis. As the data will not be analysed until the whole study is complete, there is no requirement to power the study for multiple looks. The research team will report

any undesirable events to the DSMB and the Ethics Committee. DSMB may call for an interim analysis if it is required. Termination of the clinical trial will be carried out based on the recommendation from the DSMB and/or Ethics Committee.

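### Section 4.2 names no pre-treatment covariate; pre-specifying adjustment for screening haemoglobin could add precision at little cost, though how much depends on a correlation the plan does not give

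*SAP*

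**What the plan says.** Section 4.2 gives the comparison model in one sentence: "Intervention groups will be compared using mixed effect regression models using cluster (village) as a random effect". The only model covariates it names are for Phase 2: "Analyses for phase 2 will be conducted with adjustment for weight-for-age and breastfeeding practice (exclusively/partially breastfeeding), where appropriate". Both of these arise after the randomised product has been started.

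Section 2.4.1 sets numeric limits that have to be checked for every woman before entry. They include maternal age of 19 to 35 years, "Gestational age 7-13 weeks at the time of the screening process", MUAC below 23.5 cm as an exclusion, and the exclusion "Have severe anemia (hemoglobin < 70 g/L". Section 3.2 then lists maternal haemoglobin as a secondary outcome at 35-36 weeks' gestation and at 5 months post-partum.

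On power, section 2.4.2 says of the planned numbers: "This sample size will also permit the detection of the differences in the secondary outcomes also specified below". The Table 2 row for third-trimester haemoglobin reads "12.6 1.2 0.5 0.048 1.48 132" (mean, SD, difference, ICC, design effect, sample size). The footnotes add "Required sample size per group with 80% power and alpha= 0.05" and "Design effect: based on the average size of cluster= 11". Section 2.4.2 recruits 308 women in 28 villages and takes 231 as the number retained for Phase 2.

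**The concern.** Screening haemoglobin is the pre-treatment value of a listed outcome, which is the clearest case for baseline adjustment. The plan does discuss adjustment, but names only variables that treatment could affect and leaves even those open.

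Two things are at stake. The first is precision: variation that a screening value could explain stays in the error term. This matters most for haemoglobin, where Table 2 asks for 132 per group (264 in all) and section 2.4.2 expects 231 retained, yet claims that the Table 2 differences are detectable. The second is credibility: with 28 villages randomised, some chance imbalance between arms is to be expected, and a baseline adjustment that was not pre-specified would be open to the charge of being chosen after the fact.

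**Working it through.** **Inputs.** From Table 2 for third-trimester haemoglobin: SD 1.2 g/dL, difference 0.5 g/dL, ICC 0.048, design effect (DE) 1.48, 80% power, alpha 0.05 (taken as two-sided). From section 2.4.2: 28 villages, 308 recruited, 231 retained (115.5 per arm). The correlation r between screening and third-trimester haemoglobin is not in the SAP, so it is an assumption shown over a range.

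**Reproducing the plan.** DE = 1 + (11 − 1) × 0.048 = 1.48. Required n per arm = 2 × (1.96 + 0.8416)² × 1.2² / 0.5² × 1.48 = 90.4 × 1.48 = 133.8, against 132 stated. The row reproduces closely.

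**Power with and without adjustment.** With SE = 1.2 × √(2 × DE × (1 − r²) / n), power = Φ(0.5/SE − 1.96). At n = 115.5 per arm and DE 1.48:

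| Assumed r | Required n per arm | Power, normal | Power, t on 26 df |
|---|---|---|---|
| 0 (unadjusted) | 133.8 | 0.740 | 0.707 |
| 0.1 | 132.5 | 0.744 | 0.712 |
| 0.2 | 128.5 | 0.757 | 0.725 |
| 0.3 | 121.8 | 0.779 | 0.747 |
| 0.4 | 112.4 | 0.811 | 0.780 |
| 0.5 | 100.4 | 0.852 | 0.825 |

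The last column uses a noncentral t with 28 − 2 = 26 degrees of freedom.

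**Correlation needed for 80%.** Setting 133.8 × (1 − r²) = 115.5 gives r = 0.37. With t on 26 df it is 0.45. If adjustment reduces only the within-village variance, so that the multiplier is 0.048 × 11 + 0.952 × (1 − r²) instead of 1.48 × (1 − r²), the values are 0.46 (normal) and 0.56 (t).

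**Sensitivity of the unadjusted figure** (normal approximation):

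- Number measured: the haemoglobin visit is at 35-36 weeks, before some of the losses that lead to 231. With only the 15% drop-out removed, 308 × 0.85 = 262 women give 0.79 at DE 1.48. All 308 give 0.85.
- Cluster size: 231 / 28 = 8.25 women per village, so DE = 1 + 7.25 × 0.048 = 1.348, and power at 231 is 0.78. The r needed for 80% is then 0.23 (normal) or 0.35 (t).

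**Birth length.** With SD 2.2, difference 1.0, DE 1.10 and 115.5 per arm, power = Φ(1 / (2.2 × √(1 − R²) × √(2 × 1.10 / 115.5)) − 1.96). This is 0.909 unadjusted, and 0.922, 0.935 and 0.947 if screening variables explain an assumed 5%, 10% and 15% of the variance.

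**The case against.** The strongest reply is that nothing here is an error. A model with treatment and a village random effect is a valid analysis of a cluster-randomised trial, and chance imbalance between villages is reflected in its standard error; it is not bias. That stands, and it limits the point to precision and pre-specification.

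A reader might go further and infer that adjustment would bring haemoglobin up to the 80% the plan claims. The document does not support this. It gives no correlation between screening and later haemoglobin, and at r of 0.3 or below power stays under 80% with 231 women and DE 1.48. The within-person correlation of 0.73 in section 2.4.2 concerns infant growth and cannot be borrowed. Nor is the shortfall itself established, since it depends on how many women are measured at 35-36 weeks and on the cluster size used in the design effect.

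For birth length, the objection that the gain rests on an assumed R² also stands. Eligibility narrows the range of gestational age and MUAC, and gestational age at screening is not gestational age at birth. Finally, section 2.4.1 gives cut-offs and does not state that the values were kept as numbers. Numeric limits make that likely, but it needs to be confirmed.

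None of this answers the remaining point. The plan names covariates, all of them post-randomisation, and leaves out a pre-treatment value of one of its own outcomes.

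**Conclusion.** The point holds as a precision improvement, clearest for maternal haemoglobin. On the plan's own design effect and retained number, haemoglobin power is about 0.74. Adjustment for the screening value raises it to 0.78-0.85 for an assumed correlation of 0.3 to 0.5. Reaching 80% takes r of about 0.37, or about 0.45 with t on 26 df. If more than 231 women are measured, or if the design effect is taken at the retained cluster size, the starting gap is smaller or absent. Recovery of the claimed power is therefore possible but not demonstrated. For birth length the gain is a few percentage points at most over the assumed range, from a starting power that is already adequate. The unadjusted analysis remains valid throughout.

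**What to change.** Before unblinding, add to section 4.2 wording along these lines:

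> Maternal haemoglobin outcomes will be adjusted for the haemoglobin value at screening as a fixed effect. If the length models are adjusted, the covariates will be gestational age at screening, MUAC at screening and maternal age, and no others from screening. The model with treatment and village random effect only will be reported as a sensitivity analysis for each.

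In section 2.4.2, state the correlation assumed for haemoglobin and the number of women expected at the 35-36 week visit, so that the power claim for this outcome can be checked.

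First confirm that the screening values were recorded as numbers and not only as pass or fail against the cut-off. If they were, the cost is SAP wording and a few model terms, with no new data collection.

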3.1 Study Goals

- 1) To determine whether consumption of micronutrient enriched MEC products from 8-14 weeks' gestation to delivery improves birth length in the intervention compared to the placebo group (Phase 1);
- 2) To determine if the daily consumption of micronutrient enriched crackers (MEC) by pregnant mothers from 8-14 weeks' gestation to 5 months post-partum improves attained linear growth of infants at age 5 months and linear growth velocity of infants from birth to age 5 months in the intervention compared to the placebo group (Phase 2).

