3.2 Secondary Outcomes

- 1) To determine the birth weight (measured within 24 hours after delivery);
- 2) To determine the maternal hemoglobin levels at 35-36 weeks' gestational age and 5 months post-partum (± 1 week);
- 3) To determine the maternal food intake at 35-36 weeks' gestational age, and 2 months post-partum (± 1 week), and 5 months post-partum (± 1 week);
- 4) To determine the breast milk volume and micronutrient breast milk concentrations at 5 months' post-partum (± 1 week);
- 5) To determine the infant breast milk micronutrient intake, based on breast milk volume and micronutrient breast milk concentrations at 5 months' post-partum (± 1 week);
- 6) To determine maternal micronutrient status (ferritin, transferrin serum, RBP, zinc, and selenium of mother at 35-36 weeks' gestational age and 5 months' post-partum (± 1 week), after being adjusted with the inflammation status (C-reactive protein and alpha-1-acid glycoprotein);

- 7) To determine infant micronutrient status (ferritin, transferrin serum, retinol-binding protein RBP, zinc, and selenium at 5 months old (\pm 1 week), after being adjusted with the inflammation status (C-reactive protein and alpha-1-acid glycoprotein);
- 8) To determine the infant development at 2 and 5 months old (\pm 1 week) in the intervention and control groups;
- 9) To determine the morbidity incidence rate of the mothers and infants in the intervention and control groups.

4. Data Management and Analyses

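### The Phase 2 length outcomes are not tied to one metric, and the planned model leaves out exact age, actual interval and infant sex, a loss of precision that can be removed at no cost

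*SAP*

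**What the plan says.** Three sections of the SAP describe the Phase 2 length outcomes.

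- **Section 3.1 (goals).** The aim is to see whether the crackers "improves attained linear growth of infants at age 5 months and linear growth velocity of infants from birth to age 5 months". Section 2.1 also lists growth velocity as a primary outcome. Neither gives a visit window for length.
- **Section 2.4.2 (sample size).** The calculation is "Based on an average growth velocity of 3-3.2 cm/month" and is meant "to detect differences in growth velocity of 0.70 cm between the intervention and control groups", "with power of 0.80, statistical significance of 0.05". The difference is written in cm, but the SD of 2.2 is written in cm/month. Table 2 plans 5-month length in cm: mean 63.0, SD 2.2, difference 1.0.
- **Section 4.2 (analysis).** The main outcomes "for phase 2 are attained and incremental linear growth at 5 months post-partum". The model is given as follows: "Intervention groups will be compared using mixed effect regression models using cluster (village) as a random effect". On covariates: "Analyses for phase 2 will be conducted with adjustment for weight-for-age and breastfeeding practice (exclusively/partially breastfeeding), where appropriate".

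The ±1 week visit window appears only in section 3.2. It is attached to each secondary outcome that has a stated 5-month visit, for example "To determine the infant development at 2 and 5 months old".

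**The concern.** An increment over a nominal five months and a rate per month over the actual interval are different variables. The analysis section uses the first, and the goals and the sample-size text use the second. Read literally as cm/month, a difference of 0.70 would be 0.70 × 5 = 3.5 cm over the period. Read as cm, it is 0.70 cm. Unless the SAP chooses before unblinding, the choice between increment, velocity and z-score stays open until the data are seen.

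Infants at this age also grow quickly. One seen a few days late is longer, and has a larger increment, only because of age. The two named covariates do not remove this. Weight-for-age is already standardised for age, so it does not carry the infant's age into a model for length. Boys and girls also differ in length, and that difference stays in the residual. What is at stake is precision, and a clear definition, for a primary outcome.

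**Working it through.** **Inputs.** From section 2.4.2: velocity 3–3.2 cm/month, difference 0.70, SD 2.2, within-person correlation 0.73, design effect 1.1, power 0.80, alpha 0.05 (two-sided assumed), 81 per group, and 219–228 infants expected in Phase 2. From Table 2: birth length 49.7 cm, 5-month length 63.0 cm, SD 2.2 cm, difference 1.0 cm, 114 per group, ICC 0.010, cluster size 11. Assumed, not in the documents: the ±7-day window applies to length, ages spread evenly over it, and a month is 30.44 days.

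**1. The plan's own figures.** n per group = 2 × (SD × (z₁ + z₂) / difference)² × factor × 1.1.
- Birth-length-adjusted comparison, factor 1 − 0.73² = 0.467: 2 × (2.2 × 2.802 / 0.70)² × 0.467 × 1.1 = 79.7, so 80 against 81 stated.
- Simple change, factor 2(1 − 0.73) = 0.54: 92.1, so 93. This does not match.
- Attained length, difference 1.0, 90% power: 2 × (2.2 × 3.242 / 1.0)² × 1.1 = 111.9, so 112 against 114 stated.

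The match uses 2.2 as the SD of length in cm, the same value as in Table 2. That suggests 0.70 is meant in cm, but the text does not settle it.

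**2. One week of growth for one infant.** Table 2 implies (63.0 − 49.7) / 5 = 2.66 cm/month.
- At 2.66: 2.66 × 7 / 30.44 = 0.61 cm.
- At 3 and 3.2: 0.69 and 0.74 cm.

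This is 87–105% of 0.70 and 61–74% of 1.0. If velocity is computed with a nominal 5 months, the shift is 0.61 / 5 = 0.12 cm/month.

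**3. Noise from the window.** The timing SD is 7 / √3 = 4.04 days, which is 0.353 cm at 2.66 cm/month and 0.425 cm at 3.2 (variance 0.125 to 0.181).
- Attained length, variance 2.2² = 4.84: 2.6–3.7%.
- Increment as simple change, SD 2.2 × √0.54 = 1.617, variance 2.614: 4.8–6.9%.
- Increment adjusted for birth length, SD 2.2 × √0.467 = 1.504, variance 2.261: 5.5–8.0%.

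**4. Power if this noise comes on top of the stated SD.** The increment rows use the birth-length-adjusted SD.

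| Outcome and n per group | No timing noise | Even spread, 2.66 to 3.2 cm/month | Every infant at ±7 days, 3.1 cm/month |
|---|---|---|---|
| Attained length, 114 | 90.5% | 89.8% to 89.5% | 87.5% |
| Increment, 81 | 80.6% | 78.5% to 77.6% | 72.3% |
| Increment, 109.5 (219 / 2) | 90.7% | 89.2% to 88.5% | 84.3% |

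With an even spread the loss is about 1 to 3 points. The last column is an extreme case, with a loss of up to about 8 points.

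**5. If visits are scheduled by village.** Suppose, as an assumption, that mean visit age varies between villages with an SD of 2 to 3 days. At 2.66 / 30.44 = 0.087 cm per day this adds between-village variance of 0.031 to 0.069 cm². With V the outcome variance and x the added variance, the design effect is 1 + 10 × (0.010 × V + x) / (V + x).
- Attained length (V = 4.84): 1.16 to 1.24, against 1.10 planned.
- Increment (V = 2.614): 1.21 to 1.35.

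**6. Sex.** If boys exceed girls by d = 1 to 2 cm (an assumption), the share of variance is (d² / 4) / 4.84 = 5.2% to 20.7%. If the SD of 2.2 includes this, adjustment raises attained-length power at 114 per group from 90.5% to 91.9–95.7%.

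**The case against.** A reader might infer that the visit window shifts length by about as much as the effect sought, and so could create or hide the result. The documents do not support this, for four reasons.

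- **Unlike quantities.** The 0.61–0.74 cm is one infant's shift, while 0.70 and 1.0 cm are differences between arm means. Even for one infant the comparison fits only the 0.70 target. To produce the whole effect, mean age would have to differ between arms by about 7–8 days (0.70 cm) or 10–11 days (1.0 cm), which a ±7-day window makes practically impossible.
- **No route to bias is shown.** Section 2.1 describes randomised villages, double blinding and crackers of identical appearance, so visit timing has no evident way to follow allocation. With independent timing the standard error of the arm difference in mean age is 4.04 × √(2/114) = 0.54 day to 4.04 × √(2/81) = 0.64 day, about 0.05–0.07 cm. If timing were set wholly by village it is 4.04 × √(2/14) = 1.5 days, or 0.13 cm at 2.66 cm/month. The village random effect carries that into the standard error.
- **Stated power may be right.** Table 2 labels its SDs as observed, so 2.2 cm, and likewise the source ICC, may already contain age and sex spread. Adjustment would then only gain precision.
- **Inference.** The ±1 week is stated for secondary outcomes, and cm comes from the planning inputs and not from section 4.2. Windows and measurement procedures may be in the protocol, which is not at hand.

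All four points stand, and they limit the size of the concern. They do not answer the mismatch between increment and velocity, the mixed units, or the absence of exact age, interval and sex from the stated covariates. Outcome definition and covariates are what section 4.2 sets out to fix.

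**Conclusion.** The point holds as a moderate gap in specification and efficiency. The SAP names the second Phase 2 growth outcome in two ways, mixes cm with cm/month, and plans a length model without exact age, actual interval or sex. The cost is noise, about 1 to 3 power points, with more between-village variance if visits are scheduled by village. These sizes rest on the ±1 week window applying to length, an even spread of ages, growth of 2.66–3.2 cm/month, and the noise being additional to the stated SD. Sex adjustment is likewise a gain in precision and rests on an assumed 1–2 cm difference. The primary estimate is not shown to be biased, and the sample size is not shown to be wrong.

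**What to change.** In section 4.2:

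- Define growth velocity as 5-month length minus birth length, divided by the exact interval in months between the two measurements.
- Include exact age at measurement and infant sex in the attained-length model, or analyse the length-for-age z-score and report the cm difference alongside.
- State that infants measured outside the window are analysed at their actual age.
- Use one term in place of increment and velocity across sections 2.4.2, 3.1 and 4.2, and one unit for the 0.70 difference and its SD.

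The cost is SAP wording, settled before unblinding. The planned weight-for-age adjustment needs infant age, and normally sex, so the data should already exist. There is no added burden on participants and no change to the sample size.

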2.1 Brief Description

The design of this study is a double-blind two-phase cluster randomized controlled trial to examine the effect of daily consumption of locally produced MEC (intervention group) compared to placebo crackers (control groups) in two time intervals: 1) from the second trimester of pregnancy (8-14 weeks) to delivery only; and 2) when the intervention is continued for up to 5 months post-partum, with the primary outcomes being birth length, attained linear growth, and growth velocity of the infant.

A total of 28 clusters (villages) will be randomised to either intervention or control using a randomized sequence. Selected pregnant women from these villages will receive daily interventions in the form of 7 x 75 gram micronutrient-enriched food products, made from basic ingredients of liver and chicken eggshells (Micronutrient-enriched Crackers/MEC) or placebo. The research team will give 100 grams of the same product as the respondents to the family of the respondents, so the respondents will not need to share the intervention product with the other family members. MEC or placebo will be produced locally and be identical in size, color, and packaging. MEC or placebo packages will be coded and only the production manager will know the allocated codes for the MEC or placebo packages. The production manager will be instructed to not share the code with any of the investigators involved in the trial until the primary outcomes of the study have been analyzed statistically or as requested by the Ethics Committee and/or Data Safety Monitoring Board (DSMB).

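### The Phase 2 main outcomes are to be adjusted, where appropriate, for infant weight-for-age and breastfeeding practice, both of which arise after MEC begins, and no primary model is named

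*SAP*

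**What the plan says.** Section 4.2 first gives one general model: "Intervention groups will be compared using mixed effect regression models using cluster (village) as a random effect". It names no covariates there. It then lists the outcomes: "Main outcomes for analyses for phase 1 are birth length and for phase 2 are attained and incremental linear growth at 5 months post-partum". The next sentence is the one at issue: "Analyses for phase 2 will be conducted with adjustment for weight-for-age and breastfeeding practice (exclusively/partially breastfeeding), where appropriate".

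Three other places bear on it:

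- Goal 2 in section 3.1 concerns MEC begun at 8-14 weeks of gestation and continued until the infant is 5 months old. It asks whether this, set against placebo, "improves attained linear growth of infants at age 5 months and linear growth velocity of infants from birth to age 5 months".
- Section 3.2 makes infant weight at birth an outcome of the trial: "To determine the birth weight (measured within 24 hours after delivery"). Breast milk volume at 5 months is also a secondary outcome.
- Section 2.4.2 expects losses to leave a reduced number for Phase 2, "giving a final sample size of 219-228 to assess Phase 2 outcomes".

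**The concern.** Goal 2 describes a total effect: what assignment to MEC rather than placebo does to infant length. Weight-for-age, even at birth, and exclusive or partial breastfeeding are observed after villages are randomised and after mothers have started the product. An arm coefficient adjusted for them compares infants of equal weight and feeding status, which is a different question.

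If MEC raises both weight and length, adjustment for weight removes part of the length benefit. If MEC raises weight only, the adjusted model can show a length deficit that does not exist. Because the sentence has no criterion, no age and no ranking against the general model, a reader could not tell which result was the planned one.

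**Working it through.** **The plan's own Phase 2 size.** Inputs from section 2.4.2: difference 0.70, SD 2.2, within-person correlation 0.73, power 0.80, alpha 0.05 (taken as two-sided), design effect 1.1.

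- Without the correlation: 2 × (1.96 + 0.8416)² × (2.2/0.70)² = 155.1 per group.
- Times (1 − 0.73²) = 0.467: 72.4. Times 1.1: 79.7. Rounding up to 73 before the design effect gives 80.3, hence the stated 81.
- With the variance of a plain increment, 2(1 − 0.73) = 0.54, the result is 92.1.

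The stated size reproduces from a correlation between repeated measurements. It does not rest on adjustment for weight-for-age or breastfeeding.

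**What adjustment does to attained length.** From the SAP: SD 2.2 cm and difference 1.0 cm (Table 2, 5-month length), so the true effect is 1/2.2 = 0.4545 SD; 219-228 infants, or 109.5-114 per group, divided by 1.1 for clustering. Assumed, because the SAP gives neither:

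- r, the within-arm correlation of 5-month length with the weight-for-age used: 0.4 to 0.8.
- d, MEC's effect on that weight-for-age in SD units: 0 to 0.39. The top value is Table 2's birth-weight difference, 200/514 = 0.389, a sample-size input and not an expected effect.

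Adjusted effect = 2.2 × (0.4545 − r·d) cm. Residual SD = 2.2 × √(1 − r²) cm. Power is from a two-sample t test, two-sided 0.05. Unadjusted power is 0.89-0.90.

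| d (SD) | r = 0.4: estimate, power | r = 0.8: estimate, power |
|---|---|---|
| 0 | 1.00 cm, 0.94 | 1.00 cm, >0.99 |
| 0.1 | 0.91 cm, 0.89-0.90 | 0.82 cm, 0.99 |
| 0.2 | 0.82 cm, 0.82-0.83 | 0.65 cm, 0.93-0.94 |
| 0.39 | 0.66 cm, 0.63-0.65 | 0.32 cm, 0.39-0.40 |

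Example: d = 0.2, r = 0.8 gives 2.2 × (0.4545 − 0.16) = 0.65 cm.

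**Break-even for power.** Adjusted power falls below unadjusted power when d exceeds 0.4545 × (1 − √(1 − r²))/r, which is 0.095 SD at r = 0.4 and 0.227 SD at r = 0.8. The estimate shrinks for any positive d.

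**No true effect on length.** The adjusted effect is −2.2·r·d.

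| d (SD) | r = 0.4: estimate, rejection | r = 0.8: estimate, rejection |
|---|---|---|
| 0.2 | −0.18 cm, 9-10% | −0.35 cm, 47-48% |
| 0.39 | −0.34 cm, 22-23% | −0.68 cm, 95-96% |

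**Check by simulation** (28 villages of 8 infants, ICC 0.01, village as random effect, d = 0.389). For a true 1.00 cm effect the adjusted mean was 0.66 cm with power 0.61 (r = 0.4) and 0.32 cm with power 0.36 (r = 0.8). Unadjusted, the mean was 0.99-1.01 cm with power 0.88-0.90.

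**Velocity and breastfeeding.** For the increment, the bias is −(within-arm slope of increment on weight-for-age) × d. The sign of that slope is not in the SAP and may differ between weight at birth and at 5 months, so no direction is claimed. The SAP states no MEC effect on breastfeeding practice, so that adjustment is not quantified.

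**The case against.** The best defence is that the sentence is conditional. It covers all Phase 2 analyses, including 5-month secondary outcomes, and the only model stated without a condition is arm plus village. On that reading the SAP is ambiguous rather than committed to a biased estimate. This is fair as far as it goes, but the ambiguity covers both main outcomes and nothing in the SAP resolves it. Intention to treat settles who is analysed and in which arm, not which covariates enter.

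Second, the product is coded, so choosing a model in favour of MEC would be hard. That stands; the objection is to the quantity estimated.

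Third, the largest figures are corners. The 0.39 SD comes from birth weight, and pairing it with r = 0.8 would have birth weight predict 5-month length better than the 0.73 given for repeated measurements, if that figure relates length to length. If 5-month weight is meant, 0.39 SD has no source. The r = 0.8 results at 0.39 SD should be read as extremes. With a weight effect of 0 to 0.1 SD, adjusted power is about equal to or higher than unadjusted, so loss of power is not the main argument.

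Fourth, the numbers cover one outcome and one covariate. That is true, and the conclusion does not depend on them.

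**Conclusion.** The concern holds and should be fixed before analysis. As written, the Phase 2 main result may come from a model that conditions on variables arising after exposure, and such a model does not in general estimate the effect Goal 2 asks for. For attained length, the bias is toward a smaller or negative MEC effect if MEC raises the weight-for-age used, and absent if it does not. A moderate assumed weight effect of 0.2 SD removes 18-35% of a 1.00 cm benefit over r = 0.4 to 0.8. These sizes are illustrative; the missing criterion, age and ranking of models are plain on the text. Phase 1 birth length is not affected.

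**What to change.** Replace the sentence in section 4.2 with: *For each Phase 2 main outcome (length at 5 months; length increment from birth to 5 months) the primary model contains arm as a fixed effect and village as a random effect, with no covariate measured after exposure begins.* If covariates are wanted, list by name the maternal variables measured at enrolment before the first product. Remove weight-for-age, breastfeeding practice and the conditional phrase from the primary model. Report models containing them only as labelled exploratory analyses, and state the age at which weight-for-age is taken.

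The cost is wording only, with no extra data or participants. Power for 1.0 cm attained length stays at 0.89-0.90 with 219-228 infants. One consequence should be recorded: the new sentence also excludes birth length as a covariate, whereas the stated 81 per group matches a variance of the adjusted kind, 1 − 0.73². An unconditioned increment needs about 93 per group (92.1 by the normal approximation). The expected 109.5-114 per group covers this, with power 0.86-0.87 for 0.70 cm, reading the SD of 2.2 as cm of length although section 2.4.2 writes cm/month.
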